In order to assess sensitivity of results due to missing data, a last observation carried forward (LOCF) analysis will be performed as a sensitivity analysis. In contrast to the OC dataset, the LOCF dataset will include data recorded at a scheduled visit, ie, all OC data, or, if no observation is recorded at that visit, data carried forward from the previously scheduled visit. Baseline data will not be carried forward to impute missing values for the LOCF dataset.

Change from baseline for the PANSS Total Score at Week 6 will be evaluated using ANCOVA with baseline value as covariate and treatment, trial site as main effects, on the LOCF dataset. In addition, ANCOVA with baseline value as covariate and treatment, as main effects will be performed on the OC dataset.

In case of gross violations of the MMRM model assumptions, additional supportive analyses will be provided using the generalized version of the Cochran-Mantel-Haenszel (CMH) procedure, controlling for trial site.

8.1.3 Technical Computational Details for Primary Efficacy Analysis

The following algorithm will be used for the primary analysis.

- PANSS total score is the sum of the rating scores for 7 positive scale items, 7 negative scale items and 16 general psychopathology scale items from the PANSS panel in the eSource. If less than 24 of the 30 items are recorded, the PANSS total score is not evaluable. If 24 to 29 of the 30 items are recorded, the PANSS total is equal to the mean of the recorded items multiplied by 30, and then rounded to the first decimal place.
- All scheduled visits during the 6 weeks after randomization, regardless of compliance to study assessment schedule, will be included in the analysis. If more than 1 observation falls within a particular trial day interval, then only the last observation within that interval is used in the analysis.

- All early terminated (ET) visits before week 6 will be included according to visit window.
- All ET visits 6 weeks after randomization and beyond Day 49 will not be included in the analysis.
- Evaluations occurring more than 7 days after the last double-blind dosing date will not be mapped into trial visit windows, and will be excluded from the analysis.
- Follow-up (FU) visit will not be included in the analysis.
- The week number for an ET visit will be calculated by (date of ET visit randomization/drug start date + 1) according to visit window.

Visits windows details are provided in Section 3.4.

8.1.3.1 Pooling of small sites

Small trial sites will be defined as sites that do not have at least 1 evaluable subject (evaluable with regard to the primary efficacy variable) in each treatment arm. All small sites will be pooled to form "pseudo sites" for the purpose of analysis according to the following algorithm. Small sites will be ordered from the largest to the smallest based on the number of evaluable subjects (ie, subjects who have a Baseline value and at least one post-randomization value for PANSS Total Score in the double-blind treatment period). The process will start by pooling the largest of the small sites with the smallest of the small sites until a non-small site is formed. This process will be repeated using the site left out of the previous pass. In case of ties in site size, the site with the smallest site code will be selected. If any sites are left out at the end of this process, they will be pooled with the smallest pseudo sites, or if no pseudo site exist, they will be pooled with the small site. The pooling of the small sites will be performed within each region (US, Europe [continent], Mexico).

8.1.3.2 SAS code

The MMRM analysis for the primary endpoint will be analyzed using PROC MIXED of SAS (with default REML option). Specifically, the following SAS statements will be used for the primary analysis.

Confidential - Proprietary Information2314 Mar 2023Until the information herein is released by Otsuka to the public domain, the contents of this document are Otsuka
confidential information and should not be duplicated or re-distributed without prior written consent of Otsuka.

The test of the contrast of brexpiprazole versus placebo at Week 6 will be performed by using the following estimate statement for MMRM analysis:

8.1.4 COVID-19 Pandemic Related Sensitivity Analyses

The following analyses will be performed on the Efficacy Sample to evaluate the sensitivity of the primary analysis results to the impact of pandemic. The same model (eg, with the same set of explanatory variables and the response variable) as that for the primary efficacy analysis will be used for these analyses specified below. Of note, the definition of intercurrent events and the strategy for handling intercurrent events are identical to that for the primary efficacy analysis. The date of 13 Mar 2020, date of COVID-19 pandemic announcement in the US, is taken as landmark date for analyses as considered sufficiently close to the date of significance disturbance in the other countries.

- An MMRM analysis based on the pre-COVID Efficacy Sample. The pre-COVID Efficacy Sample comprises those subjects in Efficacy Sample who had completed or discontinued the trial before 13 Mar 2020.
- An MMRM analysis based on the Efficacy Sample by using the subset of pre-COVID data. The pre-COVID data consist of the data collected before 13 Mar 2020.
- An MMRM analysis based on the non-COVID Efficacy Sample. The non-COVID Efficacy Sample comprises those subjects in Efficacy Sample who had no remote assessment of the primary endpoint.
- 4) An MMRM analysis based on the Efficacy Sample by using the subset of non-COVID data. At the subject level, the non-COVID data refer to the data that exclude his/her first remote assessment of the primary endpoint and all the assessments thereafter.
- 5) An MMRM analysis based on the Efficacy Sample by using the subset of data that exclude all remote assessments.

The point estimate along with the 95% confidence interval estimate of the treatment contrast and p-values will be presented for each of the above sensitivity analyses.

In addition, the number of face-to-face and virtual visits will be tabulated.

8 🗯

The Ukraine-Russia conflict started on 24 Feb 2022. This trial enrolled many subjects from Ukraine and Russia. However, the number of subjects from Russia and Ukraine starting treatment in the 9 weeks before the start of the conflict is very limited (N = 6), most completed the treatment and had PANSS assessment. No subject from these countries started treatment after 22 Feb 2022. Therefore, no specific sensitivity analyses will be performed.

2

£.

The following are the secondary efficacy variables in this trial:

- 1) Change in the PANSS Positive and Negative Subscale Scores
- 2) Percentage of subjects achieving response. Response is defined as at least 30% improvement from baseline in PANSS Total Score or CGI score of 1 or 2.
- 3) Percentage of subjects achieving remission. Remission is defined as a score of ≤ 3 on each of the following specific PANSS items: delusions (P1), unusual thought content (G9), hallucinatory behavior (P3), conceptual disorganization (P2). mannerisms/posturing (G5), blunted affect (N1), passive/apathetic social withdrawal (N4), and lack of spontaneity and conversation flow (N6).
- 4) Change in the Children's Global Assessment Scale (CGAS) Score
- 5) Change in the Clinical Global Impression Severity (CGI-S) scale
- 6) Clinical Global Impression Improvement (CGI-I) scale

For continuous secondary endpoints (change in CGI-S, change in CGAS, PANSS Positive Subscale score, and PANSS Negative Subscale score), an MMRM analysis with factors of treatment, trial site, visit, treatment by visit interaction, and baseline and baseline by visit interaction as covariates with an unstructured variance covariance structure will be applied based on all available data (OC dataset) from the Efficacy Sample. ANCOVA with baseline value as covariate and treatment as main effects will also be performed on the OC dataset. Data will be presented by week.

The CGI-I score will be evaluated by the Cochran-Mantel-Haenszel row mean score differ test controlling for trial site in last-observation-carried-forward (LOCF) and Observed Cases (OC) analyses. Descriptive statistics and differences between arms with 95% confidence intervals will also be presented.

Response and remission endpoints will be evaluated by the CMH General Association Test controlling for trial site, by week, in OC and LOCF analyses, for the Efficacy Sample.

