## **Trial Conduct for COVID-19**

All procedures and assessments in this protocol are to be followed to the fullest extent possible. The sponsor, in coordination with the sites, investigators, and medical monitor, will continuously monitor and evaluate the benefits and risks to subject participation in the clinical trial as it relates to COVID-19. If any protocol-specified activities were not able to be performed, or cannot be performed, due to COVID-19 considerations, refer to the COVID-19 Addendum for the appropriate measures to be followed. Appropriate measures may include but not limited to replacing in-person visits with virtual visits as deemed necessary by the investigator to ensure subject safety and maintain protocol requirements.

| Name of Sponsor: Otsuka Pharmaceutical
Development & Commercialization, Inc. |  | Protocol No.: 331-10-234    |
|---|--|-----------------------------|
|   |  | IND No.: 101,871            |
| Brexpiprazole (OPC-3-   | 4712)  | EudraCT No.: 2017-001447-12 |
| Protocol Title:   | A Multicenter, Randomized, Double-blind, Placebo- and
Active-controlled Trial to Evaluate the Efficacy of
Brexpiprazole Monotherapy for the Treatment in Adolescents
(13-17 years old) With Schizophrenia   |                             |
| Clinical Phase/Trial
Type:   | 3/Therapeutic confirmatory   |                             |
| Treatment Indication:   | Schizophrenia  |                             |
| Objective(s):   | To evaluate the short-term efficacy and safety of brexpiprazole
monotherapy in the treatment of adolescents with
schizophrenia   |                             |

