# 7 Statistical Analysis

#### 7.1 Sample Size

A sample size of 105 subjects per arm is considered adequate for this trial. It will provide at least 80% power at a nominal 2-sided alpha level of 0.05 to detect a -7.4-point reduction in PANSS Total Score change from baseline to Week 6 for brexpiprazole vs placebo assuming a standard deviation (SD) of 19. With a 1:1:1 allocation ratio, the overall sample size of this trial is planned to be 315 subjects. This will provide a sample size comparable to other similar trials.

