This is a multicenter, randomized, double-blind, placebo- and active-controlled trial designed to assess the effect of brexpiprazole compared to placebo in adolescent subjects, ages 13 to 17 years at the time of informed consent/assent and at baseline (Day 1), with a *Diagnostic and Statistical Manual of Mental Disorders - Fifth Edition* (DSM-5) diagnosis of schizophrenia and by utilizing the Kiddie Schedule for Affective Disorders and Schizophrenia-Present and Lifetime version (K-SADS-PL). The trial is planned to be conducted on an outpatient basis. Any hospitalization needed for prospective subjects, such as hospitalization needed to allow subjects to change medications in preparation for this trial requires discussion with the Medical Advisor.

This trial has a 6-week treatment double-blind period.

After a minimum 3-day washout period, subjects who continue to meet all entrance criteria (including Positive and Negative Syndrome Scale [PANSS] Total Score \geq 80) at the baseline visit (Day 1) will be randomized 1:1:1 to 1 of 3 double-blind treatment arms:

- Brexpiprazole 2 4 mg daily flexible dose
- Aripiprazole 10 20 mg daily flexible dose
- Placebo

Subjects will be randomly assigned through an interactive web response system (IWRS). Treatment assignments will be based on a computer-generated randomization code provided by the Otsuka Pharmaceutical Development & Commercialization, Inc. Biometrics Department

Brexpiprazole will be titrated to the minimum target dose of 2 mg in 8 days and aripiprazole will be titrated to the appropriate therapeutic dose consistent with the US package insert (minimum dose of 10 mg). Subjects who are unable to tolerate the minimum target dose will be discontinued. At the end of the titration period, investigators will be able to adjust the dose of double-blind IMP not to exceed 4 mg/day in the brexpiprazole treatment arm or 20 mg/day in the aripiprazole treatment arm. If subjects are not able to tolerate the minimum dose, they will be discontinued from the trial.

During the double-blind treatment phase, mandatory evaluations will take place at Day 1 (baseline), Day 4 (telephone call), and Weeks 1, 2, 3, 4, 5, and 6. However, at the discretion of the treating physician, more frequent evaluations are permitted. Data collected from subjects undergoing ad hoc evaluations may be excluded from efficacy analysis.

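### SAP 8.1.4: COVID analyses 1 and 3 select subjects by post-randomisation events and over-represent early dropouts; the effect is very small in analysis 1 and conditional in analysis 3

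*SAP*

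**What the plan says.** SAP 8.1.4 fits the primary MMRM to five subsets and reports an estimate, interval and p-value for each.

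- Analysis 1 (calendar time) uses a pre-COVID Efficacy Sample that "comprises those subjects in Efficacy Sample who had completed or discontinued the trial before 13 Mar 2020".
- Analysis 2 (calendar time) keeps the Efficacy Sample and uses only data from before that date.
- Analysis 3 (remote rating): "The non-COVID Efficacy Sample comprises those subjects in Efficacy Sample who had no remote assessment of the primary endpoint".
- Analysis 4 (remote rating) keeps the Efficacy Sample and cuts each subject's data at the first remote PANSS.
- Analysis 5 (remote rating) keeps the Efficacy Sample and removes only the remote ratings.

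The protocol's page on trial conduct for COVID-19 allows "replacing in-person visits with virtual visits as deemed necessary by the investigator" and refers to an addendum for details. Face-to-face and virtual visits will be tabulated. Neither document gives an expected dropout rate, an accrual curve or a number of remote visits. Nor does the SAP say how to read the five results if they disagree.

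**The concern.** Membership of samples 1 and 3 depends on how long a subject stayed.

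Under analysis 1, a subject who started in mid-February 2020 can enter only by dropping out before 13 Mar 2020. If still on treatment that day, the subject is removed together with every rating already made.

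Under analysis 3, a subject who leaves after two visits has had two chances of a remote rating and a completer has had six, so dropouts survive the rule more easily.

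MMRM under missing-at-random does not undo this. It recovers the Week 6 mean by borrowing from subjects with similar histories who stayed, and these rules delete such subjects along with their in-person scores. A link between dropout and response is plausible: protocol 3.7.1.5 provides for discontinuing subjects whose symptoms do not improve, and SAP 6.1.1 lists lack of efficacy among the causes of dropout. The retained sample then leans towards poor responders. If one arm loses more subjects than the other, the contrast can move for a reason unrelated to the pandemic or the rating mode, and that movement could be taken as reassurance or as alarm.

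**Working it through.** **1. The plan's own figure.** Protocol 7.1 plans 105 per arm for 80% power at two-sided 0.05 against a difference of 7.4 points, "assuming a standard deviation (SD) of 19".

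- n per arm = 2 × (1.960 + 0.842)² × 19² / 7.4² = 103.5, so 104 against 105 planned. Power with 105 is 80.6% (normal) or 80.2% (t). The figure reproduces.
- SE of the contrast = 19 × √(2/105) = 2.6 points. This is the yardstick for the shifts below, and it is larger in any subset.

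**2. Analysis 1: share of dropouts.** Assumptions, not in the documents: uniform accrual over W weeks before the landmark, and dropout proportion d with last visits spread evenly over Weeks 1 to 5 (mean 3). A completer is kept with probability (W − 6)/W, a dropout with probability (W − 3)/W on average.

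- d = 20%, W = 52: 0.2 × 49/52 = 0.188 and 0.8 × 46/52 = 0.708. The dropout share is 0.188/0.896 = 21.0%.
- Over W = 52 to 130, the share rises from 10% to 10.2–10.6%, from 20% to 20.4–21.0%, and from 30% to 30.5–31.3%.

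**3. Analysis 3: share of dropouts.** Assume each visit is remote with chance p, independently, in a fraction c of subjects. An exposed subject with k visits is kept with probability (1 − p)^k.

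- p = 10%: 0.81 after two visits, 0.53 after six. p = 20%: 0.64 and 0.26.
- p = 25%, c = 1, d = 20%: completers are kept with probability 0.75⁶ = 0.178, dropouts with the mean of 0.75¹ to 0.75⁵ = 0.458. The share is 0.2 × 0.458 / (0.2 × 0.458 + 0.8 × 0.178) = 39.1%, and 23% of the sample is left.
- p = 25%, c = 0.5: retention is 0.589 for completers and 0.729 for dropouts. The share is 0.146/0.617 = 23.6%.
- If an exposed subject is rated remotely at every visit, completers and dropouts are excluded alike and no enrichment arises.

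**4. Week 6 contrast by simulation.** 60,000 subjects per arm, true difference −7.4, Week 6 SD 19, dropout driven by the last score, unstructured MMRM; 104 weeks of accrual for analysis 1; p = 25% for analyses 3 to 5. Rates, trajectories and correlation are assumptions. Monte Carlo SE is about 0.1 on full samples and 0.25 on quarter-size samples.

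| Dropout, placebo / brexpiprazole | All data | An. 1 | An. 3, half exposed | An. 3, all exposed | An. 4, half / all | An. 5, half / all |
|---|---|---|---|---|---|---|
| 20% / 16% (equal hazards) | −7.19 | −7.19 | −7.18 | −7.37 | −7.18 / −7.42 | −7.17 / −7.22 |
| 31% / 12% | −7.48 | −7.50 | −7.57 | −9.22 | −7.41 / −7.65 | −7.33 / −7.24 |
| 17% / 28% | −7.45 | −7.41 | −7.15 | −6.58 | −7.40 / −7.32 | −7.52 / −7.52 |

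- Analysis 1 stays within 0.04 of the all-data result. With a shorter assumed accrual of 26 weeks, a separate simulation gave about 0.15.
- Analysis 3 with half exposed stays within 0.3. With all exposed it moves with the dropout imbalance: by 1.74 towards a larger effect (−9.22 against −7.48) or 0.87 towards a smaller one (−6.58 against −7.45).
- Milder assumptions with all exposed (10–20% of visits remote, dropout 31–39% on placebo and 15–18% on brexpiprazole) gave −7.7 to −8.3.
- With equal hazards and all exposed, the placebo mean moves from −13.12 to −11.35 while the contrast stays within Monte Carlo error.

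**5. Dates for a start-date rule.** SAP 3.4 counts first dose as Day 1 and maps Days 39 to 49 to Week 6.

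- A start on 31 Jan 2020 puts Day 42 on 12 Mar 2020 but Day 49 on 19 Mar 2020, after the landmark.
- For Day 49 to fall on 12 Mar 2020, the start must be 48 days earlier, on 24 Jan 2020.

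**The case against.** The strongest reply is that little rests on these two samples. Analysis 1 tests calendar time, not rating mode. Rating mode is examined three ways, and analyses 4 and 5 select nobody by remote use. No decision rule or alpha depends on any of the five. All of this stands.

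The reply continues that the larger shifts need remote visits to be frequent in every subject. Yet the plan defines a sample that had finished before 13 Mar 2020, so it expects some subjects with no pandemic-era visits. With half exposed, 0.3 points is 0.3/2.6, or about a tenth of one SE. The protocol says only that virtual visits may be used, and the addendum is not available. This also stands, as a limit on size.

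A reader might infer that the SAP's check on remote rating is itself biased, or that the bias favours brexpiprazole. The documents support neither. Analyses 4 and 5 ask the same question on the Efficacy Sample, and the direction follows whichever arm loses more subjects, which no passage states.

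Analyses 4 and 5 are not perfect either. Removing remote ratings can delete the score that led to dropout: with 50% of visits remote in all subjects and more placebo dropout, analysis 5 drifted from −7.48 to −6.97. At that level analysis 4 gave −6.62 to −7.56 across the three dropout patterns, with only 0.5⁶ = 1.6% of completers keeping a Week 6 rating.

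What the reply does not remove is the rule itself. Both samples are conditioned on post-randomisation events, and a definition without that flaw is available.

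**Conclusion.** The point holds in a limited form. Analyses 1 and 3 select on post-randomisation events and over-represent early dropouts.

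- **Analysis 1:** about one percentage point or less in dropout share with a year or more of prior accrual, and about 0.15 points or less on the contrast.
- **Analysis 3:** enrichment requires remote use that varies from visit to visit, and bias in the contrast also requires unequal dropout between arms. The shift is then about 0.3 points or less with half the subjects exposed, and larger only with frequent remote visits in all subjects.

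Every size rests on assumed dropout, accrual and remote-visit rates. It would be wrong to conclude that the primary result is in doubt: the primary test, its sample and its alpha are untouched.

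**What to change.** Change SAP 8.1.4 as follows.

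1. Define the pre-COVID Efficacy Sample by first-dose or randomisation date, whether or not the subject completed. Either require a start on or before 24 Jan 2020, so that the whole Week 6 window closes before 13 Mar 2020, or require a scheduled Week 6 date before 13 Mar 2020 (start on or before 31 Jan 2020) and drop data from 13 Mar 2020 onward.
2. Delete analysis 3, or label it supportive and report dropout by arm within the selected sample. Redefining it by start date is not useful, because it would nearly duplicate analysis 1 and would discard later subjects who were always rated in person.
3. Name analysis 4 as the main check on remote rating, with analysis 5 alongside.

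The cost is a few sentences and a changed subset flag, with no new data. The downside is that a few early dropouts leave analysis 1, and the subject-level summary of never-remote subjects is lost or demoted.

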8.2.1 Technical Computational Details for the Analysis of the Secondary Efficacy Endpoints

1. The same time windows as defined in Table 3.4-1 will be used for mapping the trial weeks are used for secondary efficacy endpoints.

- 2. Computing of Scale Scores:
- (1) The CGI-S and CGI-I of 0s will be set to missing because value 0s of CGI-S and CGI-I mean "not assessed".
- (2) PANSS positive subscale score is the sum of the rating scores for the 7 positive scale items from the PANSS panel in CRF. PANSS negative subscale score is the sum of the rating scores for the 7 negative scale items from the PANSS panel in CRF. If less than 6 of the 7 scale items of a PANSS subscale are recorded, the PANSS subscale score is not evaluable. If 6 of the 7 scale items are recorded, PANSS subscale score is equal to the mean of the recorded items multiplied by 7, and then rounded to the first decimal place.

By-visit analyses will also be conducted as previously described for the primary efficacy endpoint to inform the onset of treatment effect on these endpoints.

8.3 Subgroup Analyses

Subgroup analyses of the change from baseline in PANSS Total score at every study week will be conducted by sex, race (White and Other races), age category (< $15, \ge 15$ years) and region (US, European [continent], Mexico) using MMRM analysis with factors of treatment, visit, treatment by visit interaction, and baseline and baseline by visit interaction as covariate with an unstructured variance covariance structure.

In addition, change in PANSS Positive and Negative subscale Scores, change in CGAS Score and CGI-S scale at Week 6 (MMRM analysis with factors of treatment, visit, treatment by visit interaction, and baseline and baseline by visit interaction as covariates, (with LS Mean and 95% CI), percentage of subjects achieving response and remission (with relative risk and 95% CI), and CGI-I (difference and 95% CI) will also be computed by age category (< 15, \geq 15 years).

9 Safety Analyses

Safety will be assessed by the following secondary endpoints:

- The frequency and severity of AEs, serious AEs (clinical and laboratory), and discontinuation from the trial due to AEs
- Weight, height, body mass index, and waist circumference
- Analysis of potential suicide events recorded on the Columbia-Suicide Severity Rating Scale (C-SSRS)
- Clinical laboratory tests and urinalysis results (including serum prolactin), vital signs, physical examinations, and electrocardiogram (ECG) parameters
- Changes on the Simpson Angus Scale (SAS), Abnormal Involuntary Movement Scale (AIMS), and Barnes Akathisia Rating Scale (BARS)
- Comprehensive psychotropic side effects as assessed by the Udvalg for Kliniske Undersogelser (UKU) side effect rating scale
- Cognitive adverse effects as assessed by the New York Assessment for Adverse Cognitive Effects of Neuropsychiatric Treatment (NY-AACENT)

Safety analysis will be conducted based on the Safety Sample, which is defined in Section 5. In general, baseline of a safety variable is defined as the last observation of the variable before taking the first dose of IMP, unless specified otherwise.

Concomitant medication analyses are described under Section 7.5.

9 🏚

The start date of double-blind IMP with brexpiprazole, aripiprazole or placebo will be the first day of double-blind dosing. The number and percentage of subjects who receive double-blind IMP will be presented by week and by treatment group. Each dosing week will be based on the actual week; ie, Day 1 to 7 in Week 1, Day 8 to 14 in Week 2, etc. This summary will be performed on the Safety Sample.

The number and percentage of completers will be presented by week and by treatment group.

The mean daily dosage will be summarized by week and treatment group using descriptive statistics. The mean daily dosage per subject per week will be determined for each week of the trial. This will be calculated by dividing the sum of individual total doses by the number of days in the week interval. The summary will contain for each treatment group the number of subjects receiving double-blind IMP, and the mean and range of the mean daily dose for each week.

Extent of exposure will also be summarized by sex, race (White and All Other races), age category (< $15, \ge 15$ years) and region (US, Europe [continent], Mexico).

9

All AEs will be coded by system organ class and Medical Dictionary for Regulatory Activities (MedDRA) preferred term. The incidence of the following events will be summarized by treatment group:

- 1) Treatment-emergent AEs (TEAEs),
- 2) TEAEs by severity
- 3) TEAEs potentially causally related to the IMP,
- 4) TEAEs potentially causally related to the IMP by severity,
- 5) TEAEs with an outcome of death,
- 6) Serious TEAEs,
- 7) TEAEs leading to discontinuations of the IMP.

Treatment-emergent AE is defined as an AE that started after trial drug treatment, or if the event was continuing from baseline and was serious, trial drug related, or resulted in death, discontinuation, interruption or reduction of trial therapy.

Incidence of TEAEs will also be summarized by sex, race (White and All Other races), age category (< 15, \geq 15 years) and region (US European [continent], Mexico).

